9.3 Immunogenicity Analysis

The following statistical parameters and their 95% confidence intervals will be determined and appropriate statistical tests will be carried out to compare between booster groups:

- Percentage of participants with an IgG titre ≥ 166 Elisa units at Baseline (Visit 1), 1 month and 12 months post immunisation
- Geometric mean of pre-boost IgG titres
- Geometric mean of post- boost IgG titres
- Geometric mean of fold rise in IgG titres from pre-boost to 1 and 12 months post-boost

Exploratory outcomes:

• Ebola GP specific T cell cytokine response will be presented as means and confidence intervals, or medians and interquartile ranges if non-normally distributed. Comparisons between vaccine groups will be carried out using the appropriate parametric or non-parametric methods based on the distribution of the data.

The same will be done for IgG (parametric) and T cell (non-parametric) responses for:

- The baseline measures, between each of the three 'feeder' studies
- As sub groups for each of the three studies, comparing
 - The cell frequency/lgG titres in those boosted with AD26.ZEBOV at 1 month post boost
 - The fold rise in these measures, and proportion with three fold increase from baseline to 1 month
 - The cell frequency/lgG titres in those boosted with AD26.ZEBOV at 1 year

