4. OBJECTIVES AND ENDPOINTS

4.1 Primary Objective

To assess humoral and cellular immunity against Ebola virus glycoprotein at 1 year following a late booster dose of AD26.ZEBOV administered 3 to 4 years after receiving heterologous prime/boost of ChAd3- EBO Z /MVA –EBO Z administered at a 7 day interval

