4.2 Primary Outcome Measures

- Ebola GP specific IgG as measured by ELISA
- Ebola GP specific T cell cytokine response measured using ex vivo interferon-y enzyme-linked immunosorbent spot (ELISPOT)

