4.4 Secondary Outcome Measures

Safety

The specific endpoints for safety and reactogenicity will be actively and passively collected data on adverse events. The following parameters will be assessed for both groups:

- Occurrence of solicited local reactogenicity signs and symptoms for 7 days following the vaccination
- Occurrence of solicited systemic reactogenicity signs and symptoms for 7 days following the vaccination
- Occurrence of unsolicited adverse events for 28 days following the vaccination
- Change from baseline for safety laboratory measures
- Occurrence of serious adverse events during the whole study duration

Immunogenicity

- Humoral- Ebola GP specific IgG as measured by ELISA
- Cellular- Ebola GP specific T cell cytokine response measured using ex vivo interferon-γ enzyme-linked immunosorbent spot (ELISPOT)

Ebolavirus specific immunogenicity will be assessed by a variety of immunological assays. The primary immunogenicity outcome measures are ELISA IFN-gamma ELISPOT for T cell responses.

Exploratory outcome measures will include Ebola GP specific T cell cytokine response measured using intracellular staining technique (ICS) and multicolour flow cytometry performed with research samples collected at different study timepoints as well as other immunogenicity assays throughout the study. Antibody function will also be assessed using assays to measure neutralisation ability of antibodies to the Ebola glycoprotein. An evaluation of genetic factors associated with immune responses may also be undertaken. These may include:

- Assays to assess immunological aging, dysregulation and senescence, such as telomere length or expression of
 relevant markers and transcription factors.
- Assays to assess presence or absence of other factors affecting vaccine immunogenicity, such as antibodies against viral pathogens including cytomegalovirus.
- Determination of HLA-type

Both primary and exploratory immunology may involve collaboration with other specialist laboratories, including laboratories outside of Senegal (e.g. Europe and USA). This would involve transfer of serum/plasma and/or peripheral blood mononuclear cells (PBMC), but samples would be anonymised. Volunteers will be consented for this during the process of obtaining informed consent for the study.

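### ELISPOT is a primary outcome in sections 4.2 and 4.4, but section 9.3 treats the T-cell response as exploratory, with a data-dependent summary that may carry no confidence interval and no change from baseline to 12 months

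*Protocol*

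**What the plan says.** **Status of the outcome.** The primary objective in protocol section 4.1 is "To assess humoral and cellular immunity against Ebola virus glycoprotein at 1 year following a late booster dose of AD26.ZEBOV". Section 4.2 lists two primary outcome measures: IgG by ELISA, and "Ebola GP specific T cell cytokine response measured using ex vivo" interferon-gamma ELISPOT. Section 4.4 repeats this: "The primary immunogenicity outcome measures are ELISA IFN-gamma ELISPOT for T cell responses". The same section names intracellular cytokine staining (ICS) and flow cytometry as the exploratory T-cell work.

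**Analysis in section 9.3.** The main list, introduced as parameters with 95% confidence intervals, holds four IgG items: the percentage at or above 166 ELISA units, pre-boost and post-boost geometric means, and geometric mean fold rise to 1 and 12 months. T cells first appear under the exploratory outcomes: "Ebola GP specific T cell cytokine response will be presented as means and confidence intervals, or medians and interquartile ranges if non-normally distributed". The test is likewise to be picked from the observed distribution. The next line reads "The same will be done for IgG (parametric) and T cell (non-parametric) responses for" a set of comparisons across three feeder studies. These cover baseline measures, levels at 1 month, "The fold rise in these measures, and proportion with three fold increase from baseline to 1 month", and levels at 1 year.

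**Elsewhere.** Section 9.1 promises 95% intervals for percentages, frequencies, geometric mean titres and geometric mean fold rises. It gives no interval method for a median. The Table 1 footnote in section 7.6 puts ELISA, ELISPOT and ICS together under an exploratory heading.

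**The concern.** An outcome cannot be both primary and exploratory in one protocol. An analysis plan written from this document would inherit the conflict, because the protocol does not say which status governs.

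Two further features weaken the result:

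- **Precision.** An interquartile range describes spread between participants. It does not show how well the 1-year level is estimated. If the median branch is taken, this primary outcome may be reported with no measure of precision, in a form settled only after the data are seen.
- **Change from pre-boost.** Section 6.1 says all participants received ChAd3-EBO Z and MVA-EBO Z in 2015, so they may carry residual immunity at Day 0. A paired change shows what the late booster left behind at 1 year. The protocol plans this for IgG at 12 months but not for T cells, and gives no reason for the difference.

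**Working it through.** **1. The passages side by side.**

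| Feature | IgG (ELISA) | T-cell response |
|---|---|---|
| Status in 4.2 and 4.4 | Primary | Primary (ELISPOT); ICS exploratory |
| Status in Table 1 footnote | Exploratory | Exploratory (ELISPOT and ICS) |
| Place in 9.3 | Main list, and again in the feeder-study comparisons | Exploratory outcomes only; assay not named |
| Summary | Geometric mean with 95% CI | Mean with CI, or median with IQR, chosen from the data |
| Method label | Parametric | Non-parametric in one line, distribution-dependent in another |
| Level at 1 year | Yes | Yes, within the feeder-study comparisons |
| Change from baseline to 1 month | Yes | Yes |
| Change from baseline to 12 months | Yes, with 95% CI | None |

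The table shows three defects: the status conflict, the two incompatible rules for T cells, and the missing 12-month change. None depends on an assumption about the data.

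**2. Which assay 9.3 means.** There are two readings. If the exploratory bullet means ELISPOT, a primary outcome has been demoted. If it means ICS, which section 4.4 introduces with the same phrase, ELISPOT has no named analysis beyond the cell-frequency items in the feeder-study comparisons. Both readings need correction.

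**3. Where the 1-year T-cell level sits.** It is listed among comparisons of three feeder studies. Sections 1, 6.1 and 6.4.1 describe recruitment from EBL 06 only.

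**4. Whether a fixed summary with an interval is feasible at this size.** The synopsis expects 50% of up to 40 people: 40 × 0.50 = 20, which reproduces the stated figure. For a distribution-free interval from the k-th to the (n + 1 − k)-th ordered value,

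coverage = 1 − 2 × P(X ≤ k − 1), with X ~ Binomial(n, 0.5).

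- n = 20, k = 6: P(X ≤ 5) = 21,700 / 1,048,576 = 0.0207, so coverage = 1 − 0.0414 = 95.9% (6th to 15th value).
- n = 15, an assumed figure for losses by 1 year, k = 4: P(X ≤ 3) = 576 / 32,768 = 0.0176, so coverage = 96.5% (4th to 12th value).
- n = 40, k = 14: coverage = 96.2% (14th to 27th value).

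A median with an interval of at least 95% coverage is therefore available at any plausible size of this trial, with no check of normality.

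**5. Whether the 12-month change can be calculated.** The synopsis and Table 1 schedule immunology blood on Days 0, 7, 28 and 365. Both ends of the paired change are already collected.

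**The case against.** A reader might infer that the cellular half of the primary objective goes unanswered. The documents do not support that. Section 4.1 asks for immunity at 1 year, not for change from pre-boost, and section 9.3 lists both the baseline measures and the 1-year cell frequency. Both levels would be reported, so the missing paired change is a weakness and an unexplained asymmetry with IgG, not a breach of the objective.

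It can also be said that the label matters little. The synopsis calls the analysis descriptive, and the protocol states no alpha, power or testing hierarchy, so no confirmatory test is lost. That stands. The harm is confined to status and precision.

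A reader might want to put a figure on how often the median branch would be taken. Any such figure needs an assumed spread of ELISPOT counts, an assumed normality test and an assumed correlation between visits. The protocol gives none of these. If the non-parametric label governs, there is no data-driven switch at all. No such figure is relied on here.

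Finally, the choice of interval for a median is commonly left to the analysis plan, which is not shown and may supply one. That is fair for the method. It does not cover the primary versus exploratory conflict or the two incompatible rules for T cells, because both are fixed in the protocol text.

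**Conclusion.** The point holds in limited form and should be fixed. ELISPOT is primary in sections 4.2 and 4.4. Section 9.3 lists only IgG parameters in its main list and leaves the T-cell response, with no assay named, among the exploratory outcomes. The cellular half of the 1-year objective is answered, but only by an exploratory level inside a feeder-study comparison. That level may carry no confidence interval and has no change from baseline to 12 months beside it.

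The defect affects one of two primary outcomes, in a trial of about 20 people whose results will be read through estimates and intervals. The conclusion rests on the protocol text alone. The only assumption in the arithmetic is the number of participants with data at 1 year, and the proposed interval works at 15, 20 and 40.

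**What to change.** 1. In section 9.3, name interferon-gamma ELISPOT and move it to the main list as a primary outcome. Keep ICS and flow cytometry as exploratory.
2. Reconcile the Table 1 footnote, so that ELISA and ELISPOT are not labelled exploratory there.
3. Replace the distribution-dependent choice with one ELISPOT summary for all visits that carries a 95% confidence interval. One suitable choice is the median with a distribution-free interval (6th to 15th ordered value at n = 20), with the IQR beside it. This also removes the conflict with the non-parametric label.
4. Add the paired Day 0 to Day 365 change in ELISPOT with a 95% confidence interval, using an estimator that stays defined when a baseline count is zero. The Hodges-Lehmann estimate of the paired differences is one example.

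No significance test is needed in a descriptive study. Extending the three-fold responder proportion to 12 months is not needed either: for ELISPOT it is undefined at a zero baseline, and IgG already has 12-month measures.

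The cost is a protocol text amendment, which needs Ethics Committee approval under section 10.2.1. It needs no new visits, samples or assays.

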10. QUALITY CONTROL AND QUALITY ASSURANCE PROCEDURES

10.1 Direct Access to Source Data/Documents

The PI will provide direct access to the source documents to the EC, to the regulatory agency for inspection, and to authorised representatives nominated by the Sponsor, permitting trial-related monitoring and audits.

10.2 Quality Assurance

10.2.1 Modifications to the Clinical Trial Protocol

Any amendments to the trial that appear necessary during the course of the trial must be discussed by the investigator and Sponsor concurrently unless to eliminate an immediate hazard(s) to study participants. If agreement is reached concerning the need for an amendment, it will be produced in writing by the Sponsor and/or the investigator and will be made a formal part of the protocol. An amendment requires Ethics Committee approval. All amendments must also be transmitted to Regulatory Authorities, if applicable.

An administrative change to the protocol is one that modifies administrative and logistical aspects of a protocol but does not affect the participant's safety, the objectives of the trial and its progress. An administrative change does not require Ethics Committee approval. However, the Ethics committee must be notified whenever an administrative change is made. The PI is responsible for ensuring that changes to an approved CTP, during the period for which Ethics Committee approval has already been given, are not initiated without Ethics Committee review and approval except to eliminate apparent immediate hazards to the participant.

10.2.2 Monitoring

The Sponsor will appoint an appropriately qualified Clinical Monitor (CM) for this CT. Operations of the CM will be outlined in a Monitoring Plan agreed with the PI.

10.2.3 Initiation visit

An initiation visit will be performed before the inclusion of the first volunteer in the study. The Clinical Monitor will verify and document that the vaccines to be used for the trial has been received and that the investigational team has been properly informed about the CT and the applicable regulatory requirements.

10.2.4 Interim Visits

The CM will carry out regular interim visits. The PI or delegate commits to being available for these visits and to allow the monitoring staff direct access to participant's source documents, where existing, laboratories and CRFs. The CM is committed to professional secrecy.

During the visits, the CM may:

- Carry out evaluation of trial progress: in respect of protocol and SOP's, operating guidelines, data collection/source data verification, signature/thumb printing of consent forms, completion of documents, SAE, sample and product management, cold chain monitoring
- Inspect the CRFs, TMF and corresponding correction sheets

The CM will discuss any problem with the investigator and define with him the actions to be taken.

10.2.5 Close-out visit

A close-out visit will be performed at the end of the trial. Its goals are to ensure that:

- The centre has all the documents necessary for archiving
- All unused material has been recovered
- All vaccines have been accounted for

11. ETHICS

11.1 Declaration of Helsinki

The Investigators will ensure that this study is conducted according to the principles of the current revision of the Declaration of Helsinki

11.2 ICH GCP guidelines for Good Clinical Practice (GCP)

The Investigators will ensure that this study is conducted in full conformity with the ICH Good Clinical Practice (GCP), the requirements of the Medicines for Human Use (Clinical Trial) Regulations 2004 and its consequent approved ammendments, and local regulatory requirements.

11.3 Ethical Review

Before the inclusion of the first participant in the CT, the protocol must be approved by the Senegalese Ethics and Oxford Tropical Research Ethics Committee (OxTREC).

11.4 Informed Consent

Although consent from an individual volunteer is sufficient, participants will be encouraged to discuss the study with their husbands/wives (if married) and to have his/her agreement before consent is obtained.

The written Participant Information Sheet (PIS) is provided in French only. When the participant is iliterate, the investigator will interpret the written information in a language the volunteers understand in the presence of a indepdendant witness. When the participant is literate, he/she will read the Participant Information Sheet (PIS). The investigator involved in the informed consent discussion are trained on the study, the information sheet and consent form, and are trained to discuss the trial in the local language the volunteers understand (Wolof). The language of the consent process is documented on the consent form. If the voluteer is not able to read and write in French, an adult witness chosen by him/her, who is not part of the trial, will be present through the whole consent process and sign and date the consent form. The witness will also add the name of the volunteer and his/her date of signature.

The volunteer must give signed informed consent before being included in the trial, after having been informed of the nature of the trial, the potential risks and their obligations. There will be 2 signed informed consent forms provided (one kept by the PI or delegate and the other will be given to the volunteer).

11.5 Confidentiality

All blood tests will be identified by a unique code number only. The code key will be kept by the PI or designee who will be responsible for holding these files securely. All blood results and adverse event data will be encoded in an electronic database and stored securely by the PI or designee.

11.6 Maintaining confidentiality

Only the PI or a designated person will be able to link HIV test results. All information collected as part of the trial will be stored such that confidentiality of study participants is maintained and will not be made available to individuals outside the trial except for monitoring, auditing or required regulatory inspections. The possibility that such information could be reviewed by individuals external to the trial under these circumstances will be specified as part of the informed consent procedure.

11.7 Inducement

There may be a perception amongst volunteers of benefit from physical examination, laboratory screening and HIV testing in the current study, in addition to free health care provided during the study period for non-vaccine related medical problems. The provision of such care is necessary to ensure the required safety data is reliably collected throughout the trial. We will reimburse for transport expenses for all study participants according to standard IRESSEF CT site guidelines (Cf 11.9)

11.8 Indemnity

Compensation for any injury caused by taking part in this study will be in accordance with the guidelines of the Association of the British Pharmaceutical Industry (ABPI). Broadly speaking the ABPI guidelines recommend that 'the Sponsor', without legal commitment, should compensate participants without them having to prove that the Sponsor is at fault. This applies in cases where it is likely that such injury results from giving any new drug or any other procedure carried out in accordance with the CTP for the study. 'The Sponsor' will not compensate participants where such injury

results from any procedure carried out which is not in accordance with the CTP for the study. Where negligence can be proven, participants are still able to seek compensation. In this instance the University of Oxford is the Research Sponsor Institution.

11.9 Compensation

Volunteers will be reimbursed 10,000 F CFA for transport expenses, food and for their time lost at any scheduled study visit.

12. DATA HANDLING AND RECORD KEEPING

12.1 Data Management

The PI will be responsible for receiving, entering, cleaning, querying and storing all data that accrues from the study. The PI may delegate this responsibility to relevant staff at IRESSEF, Dakar, Senegal. The data will be entered into the participants CRFs. Data will be subsequently transferred to an electronic database for analysis.

If any changes to the Clinical Trial Protocol (CTP) are necessary during the course of the CT, a formal amendment will be presented to the Sponsor prior to submission to the relevant EC for approval unless to eliminate an immediate hazard(s) to study participant without prior ethics approval.

12.1.1 Data Capture Methods

Data capture will be on paper CRFs. The CRFs will be considered source documents. Adverse events will be tabulated in an electronic database (OpenClinica[®]) for descriptive analysis. Immunological data will be transferred to an electronic database for analysis without any volunteer identifier apart from the unique volunteer number.

12.1.2 Types of Data

Data collected will include solicited and non-solicited adverse event data, concomitant medications, clinical laboratory and exploratory immunology data. Source documents will include laboratory results and the case record file containing the case report forms for each volunteer.

12.2 Timing/Reports

Annual Safety Report: Due on anniversary of Regulatory Approval – sent to the Oxford Ethics Committee and the Senegalese Ethics Committee (CNERS).

Annual Progress Report: Due on anniversary of Ethical Approval – sent to Oxford Ethics Committee and the Senegalese Ethics Committee CNERS).

12.3 Archiving

The PI must ensure that arrangements are in place for the clinical trial site keep all clinical trial documents for at least 5 years after the completion or discontinuation of the trial, but this will be extended to meet regulatory requirements if the trial data is included in a Marketing Authorisation (MA) application.

12.4 Protocol deviations

Any unforeseen and unavoidable deviations from the protocol will be documented and filed in the study file with explanation.

12.5 Data ownership, storage, processing, sharing and transference:

The sample data will be jointly owned by all partners in the international consortium involved in the conduct of this vaccine trial. The data will be processed by a dedicated Data Manager using OpenClinica software. The data transfer will be done according to IRESSEF policy and SOP's. The sample data will be stored at Bio-bank Unit of IRESSEF and only authorised personnel including investigators, Sponsor representatives, local ethics committee members, monitors, auditors and inspectors will have access to them.

To better understand the complex antigenicity of Ebola virus and how this affects the efficacy of the vaccine, anonymised blood samples collected from the study participants may be stored for a longer period of time in the OVC Biobank ('Oxford Vaccine Centre Biobank' Southampton & South West Hampshire LREC (B) 10/H0504/25). These samples will only be used for future research purposes e.g genetic studies such as human DNA and RNA analysis to search for correlates of vaccine immunogenicity and efficacy. The samples will not be used for any commercial purpose. This information has been included in the informed consent document and the participants will be provided the option to agree or not to agree to indefinite storage of their samples. Any samples which do not have consent will be destroyed.

